8.3.2 Analysis of Primary Endpoints

PPVs on a per-patient and per-region-basis of ⁶⁸Ga-PSMA-11 PET for detection of tumor location confirmed by histopathology/biopsy will be calculated and reported along with the corresponding two-sided 95% confidence intervals. The confidence intervals will be constructed using the Wilson score method.

a) Imaging interpretation ⁶⁸Ga-PSMA-11 PET:

PET images will initially be interpreted by a board certified nuclear medicine physician or a board certified radiologist experienced in reading PET at the time of the imaging study at the institution that the study is being performed. These interpretations will not be used for final evaluation. For the data sets included in the analysis for the Primary Endpoint, imaging data will be anonymized and collected at a central site. PET data will be interpreted by three different readers in a random order at separate reading sessions. ⁶⁸Ga-PSMA PET/CT reading training set and guides will be provided and completion of this training will be required for all central review readers.

Visual interpretation:

Regions of suspected disease will be graded on a two-point scale by each reader (0=Negative or 1= Positive). A region will be judged as positive if at least one lesion in this region is visually positive.

- i) Lymph nodes will be considered positive if the ^{68}Ga -PSMA-11 uptake is focal and greater than blood pool (adjacent or mediastinal blood pool). Pelvic lymph nodes will be subclassified according to their localization as follows: R/L obturator, R/L external iliac, R/L internal iliac and other (total of 7 subgroups).
 - ii) Visceral lesions will be considered positive if the ^{68}Ga -PSMA-11 uptake is focal and greater than physiologic background activity of the involvement organ or anatomic site.
 - iii) Bone lesions will be considered positive if the ^{68}Ga -PSMA-11 uptake is focal and greater than physiologic bone marrow.
 - iv) Prostate bed and prostate lesions will be considered positive if the ^{68}Ga -PSMA-11 uptake is focal and greater than physiologic background activity of the involvement organ or anatomic site.
- b) Follow-up Imaging:

All patients will be followed up 3-12 months with conventional imaging (dedicated CT, MRI and/or bone scan). Interpretation of follow-up imaging will be performed by local read. The follow-up conventional imaging should be the same modality/modalities as the initial staging work-up to allow for reproducible and accurate comparisons.

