^{68}Ga -PSMA-11 PET positive findings will be validated as true or false positive as outlined in more detail below. False negative ^{68}Ga -PSMA-11 PET findings cannot be determined as this would require biopsies of ^{68}Ga -PSMA-11 negative but conventional or functional non- ^{68}Ga -PSMA-11 PET positive imaging lesions. Inclusion of such patients however would be violation of the inclusion criteria.

^{68}Ga -PSMA-11 PET validation based on follow-up imaging:

- i) Lymph nodes will be assessed by change in size. ^{68}Ga -PSMA-11 positive lymph nodes will be considered:
 - (1) True positive:
 - If on follow-up imaging within 3-12 months, lymph nodes seen on CT or MRI decrease by more than 30% (for patients undergoing systemic treatment of focal therapy at this site) or increase by more than 20% in short axis diameter (with a minimum of 3 mm in change in size).
 - If patients with solitary lymph node regions show a decrease of PSA by greater than 50% after targeted treatment (i.e. external beam radiation) and the lymph nodes do not change in size (less than 30% decrease or less than 20% increase in short axis diameter).
 - (2) False positive:

- If on follow-up imaging within 3-12 months, sites of initial⁶⁸Ga-PSMA-11 positive lymph node lesions seen on CT or MRI decrease by more than 30% *without* systemic therapy or focal therapy at this site.
 - If ⁶⁸Ga-PSMA-11 positive lymph node lesions do not meet the criteria for above false positive or true positive findings.
- ii) Visceral lesions (non-lymph node soft tissue or organ) will be assessed by change in size. ⁶⁸Ga-PSMA-11 positive visceral lesions will be considered:
- (1) True positive:
- If on follow-up imaging within 3-12 months, visceral lesions seen on CT or MRI decrease by 30% (for patients undergoing systemic treatment of focal therapy at this site) or increase by 20% in largest diameter.
 - If patients with solitary visceral metastasis show a decrease of PSA by greater than 50% after targeted treatment (i.e. external beam radiation) and lesions do not change in size (less than 30% decrease or 20% increase in largest diameter).
- (2) False positive:
- If on follow-up imaging within 3-12 months, sites of initial⁶⁸Ga-PSMA-11 positive lymph node lesions seen on CT or MRI decrease by more than 30% *without* systemic therapy or focal therapy at this site.
 - If ⁶⁸Ga-PSMA-11 positive lymph node lesions do not meet the criteria for above false positive or true positive findings.

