- iii) ⁶⁸Ga-PSMA-11 positive bone lesions will be considered:
- (1) True positive:
- If there was a corresponding positive sclerotic lesion on the CT portion of the ⁶⁸Ga-PSMA-11 PET.
 - If there is focal uptake seen on the baseline bone scan performed within one month of ⁶⁸Ga-PSMA-11 PET.
 - If there is a lesion noted on the initial MRI performed within one month of ⁶⁸Ga-PSMA-11 PET.
 - If within 12 months follow-up CT demonstrates development of sclerosis.
 - If within 12 months follow-up MRI demonstrates a new bone lesion.
 - If within 12 months follow-up bone scan demonstrates new focal uptake.
- (2) False positive:
- If ⁶⁸Ga-PSMA-11 positive bone lesions do not meet the criteria for true positive findings.
- iv) ⁶⁸Ga-PSMA-11 positive prostate bed and prostate lesions will be considered:

(1) True positive:

- If on follow-up imaging within 12 months, lesions seen on CT or MRI decrease by 30% (for patients undergoing systemic treatment of focal therapy at this site) or increase by 20% in largest diameter..
- If patients with prostate bed lesions show a decrease of PSA by greater than 50% after targeted treatment (i.e. external beam radiation) and lesions do not change in size (less than 30% decrease or 20% increase in largest diameter).

(2) False positive:

- If on follow-up imaging within 3-12 months, sites of initial⁶⁸Ga-PSMA-11 positive lymph node lesions seen on CT or MRI decrease by more than 30% *without* systemic therapy or focal therapy at this site.
- If ⁶⁸Ga-PSMA-11 positive lymph node lesions do not meet the criteria for above false positive or true positive findings.

c) Histopathology/Biopsy:

- i) Localization of lesions for histopathology/biopsy will be classified according to the regions in table 1.
- ii) ⁶⁸Ga-PSMA-11 positive findings are aimed to be confirmed by histopathology/biopsy if clinically feasible.
- iii) Histopathological procedures and biopsies will be performed as clinically indicated and as per institutional protocol.

(1) Positive HP/Biopsy: Confirmed sites of metastatic or tumor involvement by histopathology/biopsy will be discussed with the responsible physician/surgeon.

(2) Negative Biopsy: Patients with suspected tumor recurrence on ⁶⁸Ga-PSMA-11 PET with negative histopathology/biopsy will be handled as outlined below:

(a) Lymph nodes:

- For patients undergoing nodal dissection: Patients will be rescanned with dedicated CT or MRI to determine if the suspicious ⁶⁸Ga-PSMA-11 positive node was removed.

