8.3.3 Analysis of Secondary Endpoints

PPVs on a per-patient and per-region-basis of ^{68}Ga -PSMA-11 PET for detection of tumor location confirmed by histopathology/biopsy and conventional imaging follow-up will be calculated and reported along with the corresponding two-sided 95% confidence intervals. The paired McNemar's test will be used to compare the PPVs of ^{68}Ga -PSMA-11 PET imaging to the PPVs of conventional imaging.

Sensitivity, specificity, and NPVs on a per-patient basis of ^{68}Ga -PSMA-11 PET for detection of tumor location confirmed by histopathology/biopsy will be summarized in tabular format. Furthermore, the positive and negative likelihood ratios (LR+ and LR-) will be calculated and reported. Ninety-five confidence intervals of sensitivity, specificity, and NPV will be calculated using the Wilson score method. The comparisons of sensitivity, specificity, and NPV on a per-patient basis of ^{68}Ga -PSMA-11 PET imaging will be compared to of sensitivity, specificity, and NPV on a per-patient basis of conventional imaging using a paired McNemar's test.

Detection rates on a per-patient basis of ^{68}Ga -PSMA-11 PET stratified by PSA value (0.2 - <0.5, 0.5 - <1.0, 1.0 - <2.0, 2.0 - <5.0, 5.0) will be summarized in tabular format and compared between PSA strata using chi-square analysis. The impact of ^{68}Ga -PSMA-11 PET on clinical management in BCR patients will be evaluated using descriptive statistics.

9 Study Management

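### The imaging false-positive rules for visceral and prostate-bed lesions name only lymph nodes, so as written those two lesion types have no usable false-positive criterion

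*Combined protocol and SAP*

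**What the plan says.** The validation rules in Section 8.3.2 b) start from a two-class intent: "PET positive findings will be validated as true or false positive as outlined in more detail below". Four blocks follow.

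- **i) Lymph nodes.** There are two true-positive bullets and two false-positive bullets. The first false-positive bullet covers nodes that shrink by more than 30% without treatment. The second is a catch-all for whatever has not yet been classed.
- **ii) Visceral lesions.** The block opens with "Visceral lesions (non-lymph node soft tissue or organ) will be assessed by change in size". Its false-positive bullets are the node bullets again. The first concerns sites where "positive lymph node lesions seen on CT or MRI decrease by more than 30" per cent without treatment, and the second applies where "positive lymph node lesions do not meet the criteria for above false positive or true positive findings".
- **iii) Bone.** The single false-positive bullet is a catch-all that names its own lesion type: it applies where "positive bone lesions do not meet the criteria for true positive findings".
- **iv) Prostate bed and prostate.** The lead-in is "positive prostate bed and prostate lesions will be considered", but the two false-positive bullets are once more the node-worded ones.

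These classes are used in Section 8.3.3, where PPVs per patient and per region "confirmed by histopathology/biopsy and conventional imaging follow-up will be calculated and reported along with the corresponding two-sided 95% confidence intervals". Section 8.3.2 b) leaves the reading of follow-up imaging to the local site.

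**The concern.** PPV is the number of true positives divided by true positives plus false positives. Each lesion type therefore needs a rule that can produce a false positive. Taken as written, blocks ii) and iv) have none: their false-positive bullets speak of lesions that, by the plan's own definition or lead-in, are outside the block. That contradicts the statement that PET-positive findings will be given one of two classes.

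What is at stake is the composite (histology plus imaging) PPV. Section 3.1 describes a multi-center study and Section 1.1 foresees pooling of data between institutions for a marketing application. If one site silently corrects the noun and another applies the text as it stands, the same lesion can be classed at one site and left without a class at the other.

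**Working it through.** The plan states no figure for this point, so there is none to reproduce. The sample-size calculation in Section 8.2.1 does not depend on it. The check is a comparison of the rules.

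**1. Count of the imaging rules in Section 8.3.2 b).**

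| Block | True-positive bullets | False-positive bullets | Lesion named in the false-positive bullets | Usable as written? |
|---|---|---|---|---|
| i) Lymph nodes | 2 | 2 | lymph node | yes |
| ii) Visceral | 2 | 2 | lymph node | no |
| iii) Bone | 6 | 1 | bone | yes |
| iv) Prostate bed/prostate | 2 | 2 | lymph node | no |

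False-positive bullets in all: 2 + 2 + 1 + 2 = 7. With the wrong noun: 2 + 2 = 4. Lesion types without a usable false-positive criterion: 2 of 4.

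**2. Two test cases.**

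*A PET-positive lesion that stays the same size, with no PSA fall above 50% after targeted treatment.* No size-change or PSA criterion for a true positive is met in blocks i), ii) or iv). If the lesion is a node, the catch-all makes it a false positive. If it is visceral or in the prostate bed, the catch-all speaks only of nodes and the lesion has no class.

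*A PET-positive lesion that shrinks by more than 30% without any treatment.* The shrinkage route to a true positive is open only to treated patients. A node is a false positive under its first bullet. A visceral or prostate-bed lesion again has no class.

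A lesion that grows by more than 20% (for a node, also by at least 3 mm) is a true positive in all three blocks. The gap is therefore one-sided: only the false-positive class is lost.

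**3. Which endpoint is reached.** The composite PPV of Section 8.3.3 uses these classes directly. The histology-based primary PPV is barely touched by the noun. The written routes from a negative biopsy back to imaging, in Section 8.3.2 c)(2), are for nodes and for indeterminate bone pathology, and those two imaging blocks are intact.

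**4. Why no effect size follows.** A figure would need four inputs that the documents do not give:

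- The share of PET-positive findings classed by imaging alone. The 25% biopsy share in Section 8.2.1 refers to accrued patients, not to PET-positive findings.
- The share of visceral lesions. Table 1 puts nodal and non-nodal disease together in regions 2 and 3. Only the prostate bed has its own anticipated share (30%, Section 8.2.1).
- The share of these lesions that meet no true-positive criterion.
- What happens to a finding without a class. No section says it is left out.

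Region-level counting also dampens any effect. On PET, "A region will be judged as positive if at least one lesion in this region is visually positive". If confirmation is counted in the same way (an assumption), one unclassed lesion matters only where no other lesion in that region or patient is confirmed.

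**The case against.** The strongest reply is that this is a copying slip which the structure of the section already resolves. Each bullet sits under a false-positive heading, below a lead-in that names the right lesion type. A nodes-only reading would leave two headings with no function, and the two-class statement points the same way. Only a secondary endpoint is mainly affected. Most of this stands: the intended noun is plain, and a careful reader would probably supply it. What remains is that the text defines an endpoint and is applied by local readers at several sites. A rule of that kind should not depend on each of them making the same correction.

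A reader might also infer that the composite PPV is inflated by a large, calculable amount. The documents do not support that. It would take both the literal reading and a rule that drops unclassed findings, and the plan contains no such rule. If unclassed findings stay in the denominator as unconfirmed, this route inflates nothing.

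A reader might further infer that negative biopsies have no classification rules. That too goes beyond the text. Section 8.3.2 c)(2) works through the node cases and routes two bone results. An on-target negative biopsy is also naturally not confirmed by histopathology.

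**Conclusion.** The rules are wrong as written and should be corrected. Four of seven imaging false-positive bullets name the wrong lesion, and two of four lesion types are left without a usable false-positive criterion. Read literally, a visceral or prostate-bed finding classed by imaging could enter the composite PPV only as a true positive. The finding rests on the wording alone. The effect on the PPV cannot be derived, and it may be nil if sites read the noun as intended.

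It would be too strong to say that the intended reading removes all bias. The corrected catch-all classes as false positive any lesion that meets no true-positive criterion, and that can include a real metastasis that stays stable. The node block already works this way.

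A minor related gap does not carry the conclusion. Section 8.3.2 c)(2) states no class for an on-target negative visceral or prostate-bed biopsy, or for benign bone pathology that is neither indeterminate nor a known PSMA-positive diagnosis. Item (c) there allows repeat imaging to judge a negative biopsy but gives no criteria.

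**What to change.** In Section 8.3.2 b) ii), replace *lymph node lesions* with *visceral lesions* in both false-positive bullets. In b) iv), replace it with *prostate bed/prostate lesions* in both. Make the change before findings are classed and send it to all sites.

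The cost is four nouns in one amendment, with no added patients, procedures or data. The downside is that the composite PPV may be slightly lower than under the literal wording, because lesions meeting no true-positive criterion, some stable true metastases among them, will count as false positive.

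As a smaller step in the same amendment, the sponsor should state, before data are seen, which class applies to the negative-biopsy results that c)(2) leaves open. That statement should be consistent with the section's provision that negative bone biopsies are evaluated further.

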6.2 Prohibited Medications

There are no prohibited medications.

7 Reporting and Documentation of Results

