8.2 Determination of Sample Size and Accrual Rate

8.2.1 Sample Size and Power Estimate

The primary endpoint is to evaluate the positive predictive value (PPV) on a (1) per-patient and (2) per-region-basis (prostate bed, pelvis, extrapelvic soft tissue, and bone metastases) of ⁶⁸Ga-PSMA-11 PET for detection of tumor location confirmed by histopathology/biopsy. Based on the results of previous studies, the following distribution of disease across the four regions are anticipated (19-21):

- a) Prostate bed: 30%
- b) Pelvis: 15%
- c) Extrapelvic soft tissue: 20%
- d) Bone metastases: 35%

It is anticipated that the PPV for the four regions and for all regions combined using conventional imaging ranges from 30-60%. An overall PPV for ⁶⁸Ga-PSMA-11 PET of at most 50% will be considered as unacceptably low. Hence, the null hypothesis that the PPV is at most 50% will be tested against the alternative hypothesis that the PPV is greater than 50%. It is hypothesized that ⁶⁸Ga-PSMA-11 PET imaging on the per-region and per-patient basis will substantially increase the PPV for the four regions to at least 70%. A sample size of 75 true positives is required for rejecting the null hypothesis that the PPV is at most 50% with 90% power at the one-sided 0.01 (=0.05/5 – a Bonferroni adjustment for evaluating the PPV for the four regions and for all regions combined) significance level, assuming an average regions specific prevalence of 20%. It is expected that approximately 25% of the accrued patients will undergo a biopsy. Hence, the proposed total number of patients requiring a biopsy is 375 in

order to power the analysis at a per region level. Assuming a prevalence rate of 20% for disease in each individual region, a total sample size of 1,500 patients is required. The following table shows the attainable power levels for detecting an increase in the PPV from 50% to 70% at the one-sided 0.01 significance level for the four disease regions and for all regions combined with the proposed sample size of 1500 patients:

Table: *Attainable power levels for detecting an increase in PPV from 50% to 70% with sample size of 1,500 patients (375 biopsies)*

	Prevalence	Number of Biopsies with True Positives	Power
Prostate bed	30%	113	98%
Pelvis	15%	56	78%
Extrapelvic soft tissue	20%	75	90%
Bone metastases	35%	131	>99%
All regions combined	100%	375	>99%

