8.3 Analyses Plans

8.3.1 Analysis Population

Patients with histopathology correlates will be analyzed for the Primary Aim. All remaining patients will be analyzed for the secondary endpoints.

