 1. If ⁶⁸Ga-PSMA-11 positive lymph node is still present, a repeat biopsy can be pursued if clinically feasible and applicable, or follow-up using imaging as described above will be performed.
 2. If the corresponding node was removed, then this will be considered a False Positive.
- For patients undergoing needle biopsy: Images of the procedure will be reviewed to determine if the correct node was biopsied.
 1. If the correct node was biopsied, then a negative biopsy will be considered a False Positive.

2. If the incorrect node was biopsied, then follow-up imaging as described above will be performed.
 - (b) Bone lesions: Given the high rate of false negative biopsies for osseous metastases in patients with prostate cancer, patients with negative bone biopsies of PSMA PET positive lesions will be further evaluated:
 - If pathology demonstrates an alternative diagnoses that is known to be PSMA positive (eg Renal Cell Carcinoma metastases, Paget's disease), then this will be considered a False Positive.
 - If pathology is indeterminate, then follow-up imaging as described above will be performed to determine if the lesion is a True Positive or False Positive.
 - (c) Additionally a repeat ^{68}Ga -PSMA-11 can also be obtained, as allowable, in addition to repeat conventional imaging (CT and/or MRI) in cases of negative biopsy to determine if the biopsy was true negative or false negative.
 - (d) Although not routinely performed during standard practice, immunohistochemical staining for PSMA of tumor specimens (primary and lymph node metastases) may be performed, although not required.

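### A negative lymph-node histology is scored false positive for the primary PPV with no limit on the PET-to-tissue interval or on therapy in between, so true nodes cleared by treatment lower the PPV in the node-bearing regions

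*Combined protocol and SAP*

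**What the plan says.** The primary population in 8.3.1 is defined by the presence of tissue alone: "Patients with histopathology correlates will be analyzed for the Primary Aim". Section 8.3.2 c) leaves biopsies and surgery to clinical indication and institutional practice, and gives no maximum interval after the PET.

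For PET-positive lymph nodes with negative histology, the same section checks only whether the right node was taken. For needle biopsy: "If the correct node was biopsied, then a negative biopsy will be considered a False Positive". For nodal dissection: "If the corresponding node was removed, then this will be considered a False Positive". The dissection rule stands under the negative-biopsy item, so it concerns removal with negative histology.

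The imaging rules in 8.3.2 b) are more careful. A PET-positive node is a true positive if, on imaging at 3-12 months, "lymph nodes seen on CT or MRI decrease by more than 30% (for patients undergoing systemic treatment of focal therapy at this site"). The same shrinkage without such therapy is a false positive.

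Treatment after the scan is open. Section 6.2 states: "There are no prohibited medications". The only therapy-related exclusion in 3.3.2 is investigational therapy for prostate cancer. Change in management is a secondary objective, surveyed within 30 days of imaging and again at six months (5.1.1.1).

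Item (c) of the negative-biopsy rules allows a repeat PSMA PET with CT or MRI after a negative biopsy, to judge whether that biopsy was truly negative. It is optional.

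**The concern.** A PET-positive node may be true disease, be treated because of the scan, and be sampled later with a negative result. The tissue rule then scores the scan as wrong. The imaging rules accept that treatment can explain why a true node has changed. The tissue standard, which alone decides the primary PPV, does not.

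The primary PPV in the regions that contain nodes would then partly reflect how much treatment came between scan and tissue. That can differ between sites, and 1.1 says data are to be pooled across institutions. The two regions concerned, pelvis and extrapelvic soft tissue, have the lowest power in the plan's table (78% and 90%), so they have the least room for a downward bias.

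**Working it through.** **Inputs from 8.2.1.** The test: "the null hypothesis that the PPV is at most 50% will be tested against the alternative hypothesis that the PPV is greater than 50"%. The alternative is that PSMA PET "will substantially increase the PPV for the four regions to at least 70"%. The design is sized "with 90% power at the one-sided 0.01" level (0.05/5). The power table gives 56 findings for pelvis, 75 for extrapelvic soft tissue and 375 for all regions combined. I take these counts as the PPV denominator, although the plan labels them true positives, because that reading reproduces its power.

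**Step 1: reproduce the plan.** One-sample proportion, normal approximation:

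n = [2.326·√(0.5·0.5) + 1.282·√(0.7·0.3)]² / 0.2² = 76.6, so 77 against the stated 75.

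Power = Φ{[(p − 0.5)√n − 2.326·0.5] / √(p(1 − p))}. At p = 0.70 this gives 76.7% for n = 56 (stated 78%), 89.3% for n = 75 (stated 90%) and over 99.9% for n = 375 (stated >99%). The design is reproduced within 2 points. An exact binomial test gives less, 69.5% at n = 56 and 84.3% at n = 75. I stay with the approximation because it matches the table.

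**Step 2: effect of clearance.** Let q be the share of biopsied true lesions that were cleared by treatment before sampling and so scored false positive. Each moves from true to false positive and the denominator is unchanged, so observed PPV = 0.70(1 − q). The documents do not give q; 0 to 20% is an assumed range. The table supposes that every lesion in the region is an exposed node.

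| q | Observed PPV | Power, n = 56 | Power, n = 75 | Power, n = 375 |
|---|---|---|---|---|
| 0 | 70.0% | 77% | 89% | >99% |
| 5% | 66.5% | 56% | 71% | >99% |
| 10% | 63.0% | 35% | 47% | 99.7% |
| 20% | 56.0% | 8% | 10% | 50% |

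The observed PPV reaches the 50% null at q = 1 − 0.50/0.70 = 28.6%.

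**Step 3: not every lesion is a node.** Region 3 also holds organ and other soft-tissue metastases (2.1). If half its lesions were nodes (assumption), PPV = 0.70(1 − q/2). At q = 5% or 10% that is 68.25% or 66.5%, with power at n = 75 of about 82% or 71%. For all regions combined, if only the 15% + 20% = 35% of disease in the two node-bearing regions is exposed, PPV = 0.70(1 − 0.35q) = 68.8% or 67.6%.

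**Step 4: would dropping only late or post-therapy negatives be safe?** Assume a true PPV of 50%, 20% of lesions sampled after therapy, and half of the true ones among them cleared. Per 100 lesions, the 80 sampled before therapy give 40 true and 40 false positives. Of the 20 sampled after therapy, 5 are still histologically positive and 15 are negative. Dropping the 15 gives 45/85 = 52.9%. With denominators reduced by 15%, the one-sided rejection rate under the null rises from 1% to about 3% (from n = 75) or 10% (from n = 375). Exclusion must therefore not depend on the result.

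**The case against.** Histology is the chosen primary standard, and a correctly sampled negative node is settled by tissue. A node goes on to the imaging rules only if it is still present after dissection or if the wrong node was sampled. A reader might infer that the plan scores one and the same node both ways. It does not, and two standards may legitimately disagree. What stands is narrower: the plan recognises time and therapy as relevant to one standard and is silent on them for the other.

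A reader might also infer that any negative biopsy, or removal of a node by itself, counts as a false positive. The text does not support that. The automatic rule covers lymph nodes with negative histology. Negative bone biopsies get further evaluation, and no automatic rule is given for visceral or prostate bed lesions.

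The optional repeat imaging is a partial safeguard. It has no therapy condition and no rule for changing the classification. It cannot help a node already removed, and a node cleared by treatment may be negative on repeat PET too.

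Finally, q is unknown, and nothing suggests that treated, shrinking nodes are biopsied routinely. A q of 20% would need at least a fifth of biopsied true lesions to be treated first and then histologically cleared. This limits the size of the problem but not its direction.

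**Conclusion.** The point holds for lymph nodes. As written, a true node cleared by treatment before sampling is scored as a false positive and lowers the primary PPV in the pelvic and extrapelvic soft-tissue regions. The direction follows from the rule; the size rests on q, which the documents do not give. At an assumed q of 5-10%, the loss of power to 71-47% (n = 75) and 56-35% (n = 56) is an upper bound, since it treats every lesion in the region as an exposed node.

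A reader might conclude that the primary analysis as a whole is compromised or that false claims of success become likelier. The documents do not support either. The all-regions test keeps more than 99% power at q = 5-10%, and clearance works against the scan, so it does not inflate type I error. Late tissue could also sample disease that arose after the scan and push the PPV up, but nothing in the documents allows that to be sized. This is a worthwhile and inexpensive improvement to the analysis plan.

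**What to change.** In 8.3.1 and 8.3.2 c), define the primary PPV on tissue obtained within a pre-specified interval after the PET and before any new systemic therapy or focal therapy to that site. Apply this equally to positive and negative results. Treat other tissue as not evaluable for the primary PPV, and let those lesions be classified by the imaging rules for the secondary PPV. Report the PPV from all tissue as a sensitivity analysis, which also shows whether restricting by timing and therapy has itself changed the mix of lesions. Do not exclude only the late or post-therapy negatives.

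Record three dates per lesion: PET, tissue and start of therapy. The cost is a change of SAP wording and these dates from the chart; biopsy and treatment practice do not change. The downside is that a few biopsies leave the primary denominator.
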